6.1 Inclusion Criteria

Subjects who meet all of the following criteria (see Table 6.1-1) may be given consideration for inclusion in this clinical investigation, provided no exclusion criterion (see Section 6.2) is met.

Table 6.1-1: Inclusion Criteria

Clinical Inclusion Criteria	1) Subject is age 18 years or older. 2) Subject is willing and able to comply with study procedures and provide written informed consent to participate in study. 3) Subject with a predominantly solid lung lesion, 1 cm to 7 cm in diameter, which has been identified on chest CT (obtained within 6 weeks) with the intention to undergo a clinically indicated bronchoscopic evaluation under routine clinical care. If the lesion is partially solid (i.e. there is a ground glass component) then the solid portion must make up 80% of the lesion. 4) Subject for whom the decision to pursue biopsy has been made by the treating physician and agreed upon by the subject.
------------------------------------	---

6.2. Exclusion Criteria

Subjects who meet any one of the following criteria (Table 6.2-1) will be excluded from this clinical study.

Table 6.2-1: Exclusion Criteria

Clinical Exclusion Criteria	
 1) Subjects with pure ground glass opacity, a subsolid target lesion, and/or a ground glass opacity identified on Chest CT. 2) Subjects with lesions that include endobronchial involvement, per Chest CT. 3) Subjects who lack fitness to undergo flexible bronchoscopy and standard of care Radial EBUS-guided cytological assessment evaluations, as determined by the investigator. 4) Subjects with known coagulopathy. 5) Subjects who are pregnant or nursing mothers. 6) Subjects who are currently enrolled in another investigational study that would directly interfere with the current study, without prior written approval from the sponsor.
-----------------------------	---

7. Subject Accountability

7.1. Point of Enrollment

Point of enrollment is the time at which, following recruitment, a subject signs and dates the informed consent form.

7.2. Withdrawal

All subjects enrolled in the clinical study (including those withdrawn from the clinical study or lost to follow-up) shall be accounted for and documented. If a subject withdraws from the clinical investigation, the reason(s) shall be reported. If such withdrawal is due to problems related to investigational device safety or performance, the investigator shall ask for the subject's permission to follow his/her status/condition outside of the clinical study.

Reasons for withdrawal include physician discretion, subject choice to withdraw consent, loss to follow-up and death. Subjects may withdraw from the study at any time, with or without reason, and without prejudice to further treatment. All applicable case report forms up to the point of subject withdrawal must be completed. Additional data may no longer be collected after the point at which a subject has been withdrawn from the study or withdraws his/her consent, for whatever reason. All open adverse events should be

Confidential

closed or documented as chronic. Data collected up to the point of subject withdrawal may be used.

Subjects withdrawn prior to undergoing the diagnostic procedure with the iNod System will not count toward a center's 10 subject limit.

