2.4. Medical Equipment Description

In addition to the iNod System, all pulmonary endoscopy, or surgical suites where the study procedure is being performed must also be equipped with:

- 2.0 mm working channel bronchial scope model numbers Olympus BF-P190 or Olympus BF-MP160F
- Fluoroscopy
- All equipment necessary for Radial EBUS-guided biopsy of peripheral pulmonary lesions.
- Cytological Rapid On-Site Evaluation (ROSE)

All research centers are also required to have on-site capabilities for Chest X-Ray.

3. Objectives

To demonstrate feasibility to access, visualize, and obtain specimens adequate for cytology of lung lesions in subjects with suspected lung cancer when using the iNod System.

4. Endpoints

Primary Endpoint:

Clinical success is defined as the iNod System's ability to acquire adequate specimens of cellular matter suitable for the cytologic evaluation of targeted lung lesions, under real-time visualization.

Salvage Procedure: In case of primary endpoint failure with the iNod System, Radial EBUS -guided diagnostic sampling maneuvers (current standard-of-care) will be performed in an attempt to access, visualize, and sample targeted lung lesions.

Secondary Endpoints:

- 1) Occurrence and severity of Adverse Events related to the iNod System biopsy procedures, as well as Adverse Events related to any subsequent Radial EBUS-guided salvage procedures.
- 2) Proportion of lesions visualized during iNod Maneuvers
- 3) Proportion of lesions accessed where iNod Biopsy Needles were deployed during study maneuvers
- 4) Proportion of iNod maneuvers that acquire specimens of cellular matter for cytology

5. Design, Scale, and Duration

This study is a multi-center, prospective, single-arm human feasibility assessment.

Treatment of 15-30 subjects will take place at 2-3 clinical centers. No single clinical center will enroll in excess of 10 subjects. As the iNod System is being evaluated as a diagnostic system, study subjects are expected to be consented no more than 2 weeks prior to or up to and including the day of, but prior to, their diagnostic procedure. Subjects will exit the study, post-procedure following a pre-discharge x-ray. In the case of occurrence of a procedure-related Adverse Event, the subject will be followed through event resolution.

6. Subject Selection

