17.1. Reportable Events by Investigational Site to Boston Scientific

It is the responsibility of the investigator to assess and report to BSC any event which occurs in any of following categories:

- All Serious Adverse Events
- All Study Device, Study Procedure, and Study Procedure Anesthesia-related Adverse Events
- All Investigational Device Deficiencies
- Unanticipated Adverse Device Effects
- New findings/updates in relation to already reported events

When possible, the medical diagnosis should be reported as the Event Term instead of individual symptoms.

If it is unclear whether or not an event fits one of the above categories, or if the event cannot be isolated from the device, procedure, or anesthesia, it should be submitted as an adverse event and/or device deficiency.

Any AE event required by the protocol, experienced by the study subject after informed consent and once considered enrolled in the study (as defined in study subject classification section), whether during or subsequent to the procedure, must be recorded in the eCRF.

Underlying diseases are not reported as AEs unless there is an increase in severity of frequency during the course of the investigation. Death should not be recorded as an AE, but should only be reflected as an outcome of one (1) specific SAE (see Table 17.2-1 for AE definitions).

Refer to Section 16 for the known risks associated with the study device(s).

Adverse event definitions are provided in Table 17.1-1. Administrative edits were made to combine definitions from ISO 14155-2011 and MEDDEV 2.7/3 12/2010.

Table 17.1-1: Safety Reporting Definitions

Term	Definition
Adverse Event (AE) Ref: ISO 14155-2011 Ref: MEDDEV 2.7/3 12/2010	Any untoward medical occurrence, unintended disease or injury, or any untoward clinical signs (including an abnormal laboratory finding) in subjects, users or other persons, whether or not related to the investigational medical device. NOTE 1: This includes events related to the investigational medical device or comparator. NOTE 2: This definition includes events related to the procedures involved (any procedure in the clinical investigation plan).

Table 17.1-1: Safety Reporting Definitions

Term	Definition
	NOTE 3: For users or other persons, this definition is restricted to events related to the investigational medical device.

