20.4 Criteria for Suspending/Terminating a Study Center

Boston Scientific Corporation reserves the right to stop the inclusion of subjects at a study center at any time after the study initiation visit if no subjects have been enrolled for a period beyond 3months after center initiation, or if the center has multiple or severe protocol violations/noncompliance without justification and/or fails to follow remedial actions.

In the event of termination of investigator participation, all study devices and testing equipment, as applicable, will be returned to BSC unless this action would jeopardize the rights, safety or well-being of the subjects. The IRB/EC and regulatory authorities, as applicable, will be notified. All subjects enrolled in the study at the center will continue to be followed through resolution of any procedure-related adverse events unless they are considered to endure in a chronic nature. The Principal Investigator at the center must make provision for these follow-up visits unless BSC notifies the investigational center otherwise.

21. Publication Policy

In accordance with the Corporate Policy on the Conduct of Human Subject Research, BSC requires disclosure of its involvement as a sponsor or financial supporter in any publication or presentation relating to a BSC study or its results. In accordance with the Corporate Policy for the Conduct of Human Subject Research, BSC will submit study results for publication (regardless of study outcome) following the conclusion or termination of the study. Boston Scientific Corporation adheres to the Contributorship Criteria set forth in the Uniform Requirements of the International Committee of Medical Journal Editors (ICMJE; <http://www.icmje.org>). In order to ensure the public disclosure of study results in a timely manner, while maintaining an unbiased presentation of study outcomes, BSC personnel may assist authors and investigators in publication preparation provided the following guidelines are followed.

1. All authorship and contributorship requirements as described above must be followed.
2. BSC involvement in the publication preparation and the BSC Publication Policy should be discussed with the Coordinating Principal Investigator(s) and/or Executive/Steering Committee at the onset of the project.

3. The First and Senior authors are the primary drivers of decisions regarding publication content, review, approval, and submission.

22. Bibliography

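### Protocol Section 7.2 ends safety data collection after every withdrawal, even where consent still stands, and does not fit the follow-up and reporting rules in Sections 5 and 17

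*Protocol*

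**What the plan says.** **Protocol Section 7.2 (Withdrawal).** The reasons listed are physician discretion, the subject's own withdrawal of consent, loss to follow-up and death. One rule then covers them all: "Additional data may no longer be collected after the point at which a subject has been withdrawn from the study or withdraws his/her consent", and the sentence adds that the reason makes no difference. Adverse events still open should be "closed or documented as chronic". Case report forms must be completed up to withdrawal, and "Data collected up to the point of subject withdrawal may be used". There is one special provision: "If such withdrawal is due to problems related to investigational device safety or performance", then "the investigator shall ask for the subject's permission to follow his/her status/condition outside of the clinical study".

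**Protocol Section 5.** "In the case of occurrence of a procedure-related Adverse Event, the subject will be followed through event resolution". No exception is made for withdrawn subjects.

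**Protocol Section 17.1 and Table 17.3-1.** Sites must report all serious events, all events related to the device, procedure or anesthesia, and "New findings/updates in relation to already reported events". Reportable events after consent go into the eCRF. Table 17.3-1 keeps reporting of adverse events and serious adverse events in force through the end of the study.

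**Protocol Section 8.7.** A call at 7 (±1) days looks for late safety events.

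**Protocol Section 20.4.** When a center is closed, "All subjects enrolled in the study at the center will continue to be followed through resolution of any procedure-related adverse events", except for events considered chronic.

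**SAP.** Section 3.1 reports the proportions of patients with adverse events and serious adverse events. Section 4.1 lists secondary endpoint 1, the occurrence and severity of related events. Section 4.6.3 summarizes disposition. No rule covers adverse events in withdrawn subjects.

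**The concern.** Withdrawal of consent and withdrawal by someone else are different situations. Only in the first has the subject refused anything. Section 7.2 names both and treats them alike, so a subject taken out by the physician the day after the procedure, with consent intact, would get no Day 7 call and no further entries in the study record. Sections 5 and 17 appear to require the opposite for the same subject. Section 12 forbids investigators to deviate except in an emergency, so a site has no sanctioned way to choose between them.

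Secondary endpoint 1 is the only safety endpoint in a study that documents the first human use of the system. Events that go unrecorded after withdrawal can lower the counts and grades reported there but cannot raise them. Withdrawals prompted by a device problem deserve particular care, yet for these Section 7.2 places follow-up outside the study and states no route by which the findings reach the eCRF.

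**Working it through.** The plan gives no figure to reproduce here. The check is a comparison of texts, followed by an illustration of size.

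**1. Does the bar reach subjects whose consent stands?** Yes. It applies to a subject who has been withdrawn or who withdraws consent, and physician discretion is on Section 7.2's own list of reasons.

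**2. Do the other rules exempt such subjects?**

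| Place | Rule | Exception for withdrawal | Relation to 7.2 |
|---|---|---|---|
| Section 5 | Follow procedure-related events to resolution | None | Direct conflict |
| Section 17.1 | Record events after consent and report updates | None | Conflict over recording and updating |
| Table 17.3-1 | Report adverse events and serious adverse events through end of study | None | Conflict over recording and updating |
| Section 8.7 | Safety call at 7 (±1) days | None | Call not made if 7.2 is followed |
| Section 20.4 | Follow to resolution after center closure unless chronic | Not about withdrawn subjects | No direct conflict; similar intent |

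**3. What can be lost?** Secondary endpoint 1 counts occurrence and severity, not resolution. An event recorded before withdrawal stays in the data. Two things remain exposed: a new related event between withdrawal and the Day 7 call, and a later change in severity or escalation to a serious event.

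**4. How large is one loss?** Inputs: 15 to 30 treated subjects (Protocol Section 5). Assumptions: one withdrawn subject has one missed event and no other event of that kind, the subject stays in the denominator, and nobody else has such an event.

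Shift in the proportion = missed events / n:
- n = 15: 1/15 = 6.7 points
- n = 30: 1/30 = 3.3 points

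Exact (Clopper-Pearson) 95% upper limits:
- No events: upper limit = 1 − 0.025^(1/n). For n = 15 this is 21.8%; for n = 30 it is 11.6%.
- One event: the upper limit is the p that solves (1 − p)^n + n·p·(1 − p)^(n−1) = 0.025. For n = 15 this is 31.9%; for n = 30 it is 17.2%.

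| n | Reported if the event is lost | Reported if it is captured |
|---|---|---|
| 15 | 0/15, upper limit 21.8% | 1/15 = 6.7%, upper limit 31.9% |
| 30 | 0/30, upper limit 11.6% | 1/30 = 3.3%, upper limit 17.2% |

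The documents give no withdrawal rate. Two such subjects would shift the proportion by 13.3 points (n = 15) or 6.7 points (n = 30); three would shift it by 20.0 or 10.0 points. The SAP plans no intervals for safety proportions, so the limits above serve only to show scale.

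**The case against.** The best defense is that Section 5 is the general rule and Section 7.2 the specific exception, since a withdrawal clause normally limits general follow-up. For subjects who withdraw consent this succeeds: ending collection is what they asked for. It does not explain why the same bar should cover subjects withdrawn at the physician's discretion. One could also take the end of the study in Table 17.3-1 to mean the subject's own exit, but the table does not say so.

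Several stronger readings are tempting, and the documents do not support them.

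- A reader might infer that Sections 17.1 and 20.4 are further follow-to-resolution rules that 7.2 contradicts. Section 17.1 is a recording and updating duty. Section 20.4 concerns center closure and exempts chronic events, which brings it close to 7.2.
- A reader might infer that 7.2 forces a false outcome for every open event. The clause says what should be done, closed is not defined and may mean closing the record, and the eCRF outcome codes are not in the documents. What can be said is that the text names no category for an acute event still ongoing at withdrawal.
- A reader might infer that an event leading to withdrawal drops out of the safety tables. It does not; data up to withdrawal are kept.
- A reader might infer that findings after a device-related withdrawal never reach the sponsor. The investigator must ask permission to follow the subject, and Section 17 contains no exemption. The text shows only that no route into the database is stated.

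It also stands that exposure is one procedure with about a week of follow-up, that device failure during the procedure leads to salvage rather than withdrawal, and that the analysis is descriptive. Withdrawals in that window may be few.

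**Conclusion.** The point holds as an internal conflict with a limited but one-directional consequence. Section 7.2 stops safety data for subjects who have not withdrawn consent, and this cannot be squared with Section 5 or with the recording and updating duties in Section 17.1 and Table 17.3-1. New related events up to Day 7, and later worsening of known events, could go unrecorded, which could understate secondary endpoint 1.

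One might go further and say that the adverse event proportions are biased downward. The documents do not establish that: they give no withdrawal rate, and none of the withdrawals need involve a late event. The shift of 6.7 points at 15 subjects or 3.3 points at 30 rests on the assumption of exactly one lost event. In a sample this small, that one event could decide whether any serious event is reported. The passages should therefore be reconciled.

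**What to change.** Reconcile Protocol Section 7.2 with Sections 5 and 17.1:

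1. Limit the bar on data collection to subjects who withdraw consent and decline safety follow-up.
2. For all other withdrawals, keep the Day 7 safety contact and the updates on adverse and serious adverse events, entered in the study database. State that this includes withdrawals for device safety or performance.
3. Record each open event by its status at last contact, with ongoing at withdrawal as an allowed entry.
4. In the SAP, report the number of treated subjects without a Day 7 contact beside the adverse event table, so that a reader can see how much late follow-up is missing.

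The cost is a wording amendment and a few more calls by staff who already make the Day 7 call. No new visit or procedure is needed. The consent form was not available for this review, so whether its text needs a matching change should be checked.

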7.3. Enrollment Controls

The risk of over-enrollment is minimized by utilizing a limited number of clinical centers and maintaining close communication with study centers.

8. Study Methods

8.1. Data Collection

Boston Scientific
iNod Feasibility Clinical Protocol
91122035 Rev/Ver AA
Page 18 of 44

Table 8.1-1: Data Collection Schedule

Procedure/Assessment	Study-Specific (iNod) or Standard of Care (SOC)	Screening	Baseline	Procedure	Completion / Study Exit
Informed consent form, including informed consent signature date	iNod		X		
Demographics, including date of birth, and gender	iNod		X		
Physical Exam	iNod				
HCG Pregnancy Testing for women of childbearing potential	iNod		X		
Historic Diagnostic Chest CT	SOC	X			
Confirmed at enrollment, but per standard of care within 6 weeks of procedure					
Historic PET Results	SOC	O			
Medical history	iNod		X		
Sedation	SOC			X	
iNod System Diagnostic Procedure(s)	iNod			X	
iNod Ultrasound (US) Images including lesion visualization and needle visualized in the iNod US Field	iNod			X	
Fluoroscopic Images during iNod Maneuver(s)	iNod			O	
ROSE (Rapid on-site Evaluation) of obtained specimen (s)	SOC			X	
Complete Cytology of obtained specimen(s)	SOC			X	X
Standard of Care Diagnostic Procedures (as indicated as required)	SOC			O	
Standard of Care US Images including lesion visualization and needle visualized in the iNod US Field	SOC			X	
Fluoroscopic Images during Standard of Care Maneuver(s)	SOC			O	
ROSE (Rapid on-site Evaluation) of obtained specimen (s)	SOC			X	
Complete Cytology of obtained specimen(s)	SOC			X	X
Discharge X-ray	SOC				X
Device, Procedure, and Anesthesia-related adverse events assessment, including Day-7 Post-Procedure Call	iNod			X	X

X = required; O = optional but recommended

Boston Scientific
 iNod Feasibility Clinical Protocol
 91122035 Rev/Ver AA
 Page 19 of 44

8.2. *Study Candidate Screening*

Potential study candidates will be selected based on the investigator's review of subject referrals for evaluation of their medical history and assessment of candidate's Chest CT, completed within 6 weeks of study procedure, that indicate the presence of a suspected solid peripheral pulmonary nodule between 1cm and 7cm in size.

Only subjects that meet the CT and all other Inclusion Criteria should move forward to the Informed Consent process. All subjects screened and consented will be patients of the investigator(s).

8.3. *Informed Consent*

Written Informed Consent must be obtained for all subjects who are potential study candidates. Subjects will be asked to sign the Informed Consent form before any study-specific tests or procedures are performed. The Informed Consent form is study-specific and must be approved by the study Institutional Review Board (IRB)/Ethics Committee (EC) and Competent Authority, as applicable.

8.4. *Baseline*

Must be conducted no more than 2 weeks before or on the day of (preceding) iNod System procedure.

- Informed Consent
- Eligibility Criteria Assessment
- Demographics
- Bronchoscopy History
- Physical Exam including Height & Weight
- Confirmation of a peripheral pulmonary lesion, per historic Chest CT (within 6 weeks of procedure)

Baseline attributes of the target lesion will be recorded:

- Location of Lesion
- Size of Lesion
- Attributes of Lesion (e.g. solid or partial ground glass)

8.5. *iNod Diagnostic Procedure*

The subject will be prepared for the study procedure under sedation as per current standard of care.

The investigator will perform a bronchoscopic assessment of all lobes of the lung and confirm that there are no contraindications to continue with the iNod System procedure.

iNod System components are supplied to the investigative centers for the conduct of this clinical study by Boston Scientific, free of charge. Each iNod System component will be utilized only to the extent and use limits, defined in the Investigator Brochure. Multiple (a minimum of 4) iNod Ultrasound Catheters and (a minimum of 4) iNod Biopsy Needles are to be available at the commencement of a study procedure.

All iNod System components utilized during a procedure will be recorded, by serial number, to insure device accountability. The model number(s) of the bronchoscope(s) being utilized will also be captured.

The following procedural data will be captured:

- Timing of the total duration of the case, from initial introduction of the bronchoscope to final removal of bronchoscope
- Each iNod Maneuver will be timed from introduction of the iNod Biopsy Needle catheter, pre-loaded with the iNod Ultrasound Catheter, through the removal of the iNod Biopsy Needle.
- Intra-procedural Attributes of the target lesion(s) will be recorded:
 - Location of target lesion (e.g., RB¹, RB², RB³, etc.)
 - Assessment of concentric lesion vs. eccentric lesion
 - Assessment for positive bronchus sign

Imaging to be captured during the iNod System maneuvers, as identified with the serial number of the iNod Imaging System and iNod Biopsy Needle being utilized for each maneuver, will be collected as follows:

- Ultrasound image of the target lesion
- Ultrasound image of the deployed iNod Biopsy Needle at the target lesion
- Supplemental fluoroscopic images, if collected, should also be retained and similarly associated to the specific maneuver by documenting the serial number of the iNod Biopsy Needle being used for that specific procedure

Rapid on-site evaluation (ROSE) will be completed for all obtained specimens. Results will be associated with the serial number of the iNod Biopsy Needle being used for each unique specimen. ROSE interpretations, “adequate (for cytologic evaluation)” or “inadequate (for cytologic evaluation),” will be recorded. Collected specimens will undergo cytologic evaluation following the iNod procedure and final cytologic results will be reported in the study database.

The following situations would indicate the need to abandon the iNod System Procedure and proceed to salvage:

- If the iNod System is unable to physically reach the lesion, as evidenced by the absence of an ultrasound image of the lesion with the iNod System.
- If 3 separate aspirated specimens obtained from the target lesion with the iNod System result in “inadequate (for cytologic evaluation),” the investigator should stop iNod maneuvers and proceed to salvage.

